Title: Effect of long acting antihistamine on opioid- induced pruritus: A double-blind placebo controlled study

PI: [name]

NCT #: 01825655

Unique Protocol ID: HM20003779

Document approval date: August 26, 2015

Document Type: Protocol and SAP

Protocol

Effect of long acting antihistamine on opioid- induced pruritus: A double-blind placebo controlled study.

Principal Investigator: [name]

Co-investigators: [name]

[name]

[name]

[name]

[name]

[name], PA

[name], NP

Correspondence:

[name]
Assistant Professor of Pediatrics
Division of Allergy & Immunology
Virginia Commonwealth University School of Medicine
[name]
[contact]
[contact]

Background and Significance:

Opioids are commonly used in the treatment of moderate-severe pain. Pruritus is a common adverse effect of this class of medications, occurring in up to 10% of subjects treated with oral or intravenous opioids. [1]. The prevalence goes up with the dose of opioid being used [2]. The exact mechanism for the pruritus is unknown but there are two principal theories: A peripheral effect mediated by histamine released via direct mast cell degranulation by opioids; and a central mechanism mediated by μ opioid receptors in the nervous system [3, 4].

Currently, there is no standardized treatment for opioid induced pruritus. Most studies conclude that opioid antagonists are the best treatment; however, they also decrease the analgesic effect. A recent study has compared Odansetron and diphenhydramine treatment for pruritus in women who received intrathecal opioids and found them equally effective. [5]. This study was in adults receiving intrathecal opioid. There are no pediatric studies looking at effective treatment options for opioid-induced pruritus. As a consequence, the usual practice is to discontinue the opioid and use an alternate drug for analgesia. There are no prospective double blind studies available that have looked at the effect of a second-generation, non-sedating, long- acting antihistamine on opioid induced pruritus in children.

Hypothesis:

Histamine is the primary mediator responsible for pruritus induced by oral or intravenous administration of opioids. A second generation, long acting antihistamine will be effective at relieving the pruritus and allowing continued therapy with opioids.

Specific aims:

- Our primary objective is to assess the efficacy of a long- acting antihistamine, Cetirizine, on opioid- induced pruritus in a double-blind, placebo controlled study. The primary outcome will be number of treatment failures between the treatment and placebo groups. Treatment failure is defined as persistent itch score of > 3 3hrs after receiving the intervention.
- 2. Our secondary objectives are to analyze:
 - The correlation between baseline serum tryptase levels and the occurrence of opioid- induced pruritus.
 - The effect of age, race, sex on opioid induced pruritus and the influence of these parameters on antipruritic effect of the drug.

Methods:

Subject recruitment:

This study is a randomized, double blind placebo controlled study. Subjects 6-18yrs of age, requiring treatment with oral or intravenous opioids will be recruited from the pediatric inpatient units at Children's Hospital of Richmond at VCU.

Inclusion criteria:

- Children age 6-18yrs on opioids who develop pruritus and are willing to participate in the study

Exclusion criterias:

- Children with history of chronic urticaria
- Children with other chronic pruritic condition like eczema, contact dermatitis, psoriasis
- Children with known hypersensitivity to cetirizine/zyrtec
- Children on second generation antihistamine 1 week prior to the study recruitment
- Children who are unwilling or unable to swallow the capsule.
- Children with chronic liver or kidney disease

Study Design:

After obtaining an informed consent from the parent or guardian, and an informed assent from children ages 12 years and above, serum tryptase levels will be drawn at baseline. For subjects whose baseline tryptase could not be drawn prior to the onset of itch symptom, a second attempt will be made either 24hrs after being symptom free or at a later date either in the inpatient or outpatient setting when they are free of symptoms.

Subjects who develop pruritus will have a baseline itch score measured at the onset of the itch symptom. Subjects with itch score of ≥ 3 will be randomized in a double blind fashion to the treatment group with cetirizine 10 mg once daily or to the placebo group. A tryptase level will be obtained 15-60 minutes after the onset of itching. Subjects will have itch scores measured at two time points from receiving the intervention, one at 3hours and other at 12 hours. Subjects will be allowed to receive rescue Diphenhydramine (Benadryl) 3 hours post intervention at the discretion of the treating physician.

Treatment failure is defined as an itch score of ≥3 at 3 hours post intervention and will result in discontinuation from the study. Successfully treated subjects will have a second itch score measured at 12 hours post intervention to analyze the persistence of antipruritic effect of the intervention. The numbers of treatment failures in each group are recorded. The total number of rescue Benadryl doses in each group will also be

recorded. The opioid dose, interval and total doses that each subject receives will be recorded. Patients whose treatment has been successful in controlling the pruritus (itch score ≤ 2) will continue in that arm for a maximum of 12 hours or till discharge whichever is earlier. Patients may drop out of the study at any time. The reason for dropping out will be recorded. At the conclusion of the study, patients will be reassessed by the primary team for further need for any anti-pruritic medications.

Primary Outcome

Number of treatment failures in the study group versus the placebo group at 3 hours post randomization

Secondary Outcomes:

- 1. Number of drop outs in the study group versus the placebo group at the end of the study period.
- 2. Tryptase levels (Total and mature) in subjects who develop opioid-induced pruritus versus those who do not.
- 3. Change in Tryptase levels (Total and mature) from baseline in subjects who develop pruritus
- 4. Effect of age, race, and sex on the incidence of opioid-induced pruritus
- 5. Effect of age, race, and sex on response to cetirizine in subjects with opioid-induced pruritus.
- 6. Change in the baseline itch score between treatment and the placebo group.
- 7. Number of rescue Benadryl doses between treatment and the placebo group.

Preliminary Results:

Based on our experience (n=16) over the last few months, 37% (n=6) of patients treated with opioids in the inpatient setting develop pruritus. Of those 6 patients, 66.6% were successfully treated with an antihistamine and were able to continue treatment on the same opioid.

Statistical Method:

Data will be analyzed using Chi square, student t-tests and Mann-Whitney U test (for non-parametric data) where appropriate. A p value of <0.05 will be considered significant.

Assuming a 50% reduction in the failure rate to be clinically significant, a sample size of 66 confers a power of 0.8 at α =0.05. Assuming a 10% drop out rate in each group a total of 73 patients will be recruited.

Time line:

We plan to recruit at least 1 patient per week for this study. The study should be completed in 2years. There is a real chance of completing this study much earlier than the 2 year time frame.

Investigator responsibilities:

- The study will be approved by the Western Institutional Review Board
- Conduct the study smoothly and effectively
- Report any adverse effects to McNeil Pharmaceuticals.
- At the completion of the study the data will be presented to McNeil before sending in for publication.

Future research direction:

- 1. To analyze the effect of antihistamine on opioid-induced itching in a much larger sample size.
- 2. To investigate titration prick skin testing to opioid as a predictor of opioid-induced itching.

Limitation of the study:

1. Itch scale is subjective and hence there is no objective way to assess improvement in itching

Sample size calculation

Sample sizes for an α = 0.05 significance level with a two group continuity corrected χ 2 test of equal proportions – 1 sided test, equal sample sizes in each group

Placebo Group	Treatment Reduction	Treatment Group	Sample Size Per Group 80% Power	Sample Size Per Group 90% Power
0.3704	10% Reduction	0.3333	2,102	2,890
0.3922	15% Reduction	0.3333	857	1,174
0.4167	20% Reduction	0.3333	440	599
0.4444	25% Reduction	0.3333	255	346
0.4762	30% Reduction	0.3333	159	214
0.5556	40% Reduction	0.3333	70	90
0.6667	50% Reduction	0.3333	33	43
0.8333	60% Reduction	0.3333	15	19

ITCH SCORE

	1=No		3= Moderate	4= Severe pruritus
	pruritus	(no intervention	pruritus	
		necessary)	(intervention	
			necessary)	
3hrs				
12hrs				

Description of the scores:

- 1. No pruritus- absence of any itching
- 2. Mild pruritus- presence of itching in only one location of the body (e.g. faces or arm). No intervention necessary as assessed by the investigator and the patient agreeing to the decision. Usually the itching is not relieved by the patient and only reported after being prompted by the investigator/
- 3. Moderate pruritus- presence of itching in more than one location, typical in 2 locations (e.g. arms and thorax). Intervention necessary as assessed by the investigator and the patient.
- 4. Severe pruritus- severe itching which involves almost the entire body and often disturbing the patient.

Score of \geq 3-included in the randomization

Improvement is a score of ≤ 2 at 3hrs

References:

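### The sole primary endpoint has two cut-offs: failure is an itch score above 3 in Specific aims but 3 or more in Study Design

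*Combined protocol and SAP*

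**What the plan says.** The primary objective, under Specific aims, defines the event: "Treatment failure is defined as persistent itch score of > 3 3hrs after receiving the intervention". Study Design defines the same event again with a different threshold: "Treatment failure is defined as an itch score of ≥3 at 3 hours post intervention".

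Four other places bear on which threshold is meant:

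- Entry, in Study Design: "Subjects with itch score of ≥ 3 will be randomized in a double blind fashion".
- Success, in Study Design: "Patients whose treatment has been successful in controlling the pruritus (itch score ≤ 2) will continue in that arm".
- Improvement, at the end of the itch score description: "Improvement is a score of ≤ 2 at 3hrs".
- The Primary Outcome entry, which counts failures without giving a cut-off: "Number of treatment failures in the study group versus the placebo group at 3 hours post randomization".

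The itch score form has four levels, from 1 (no pruritus) to 4 (severe), with rows for 3 and 12 hours. Level 3 is moderate itch for which intervention is judged necessary.

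**The concern.** On a four-level scale, a score above 3 can only be 4. The two definitions therefore differ for every child who scores exactly 3 at 3 hours. This is not a rare corner of the scale: all participants enter at 3 or 4, so a 3-hour score of 3 is what an unchanged child who entered at 3 will show.

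This is the only primary outcome, and no section says which definition governs. The form records the full score, so either count can be derived from the same data and the choice could be made after the results are seen. The planning rates do not settle it either. Preliminary Results reports treatment success with neither an itch score nor a time point: "Of those 6 patients, 66.6% were successfully treated with an antihistamine and were able to continue treatment on the same opioid".

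**Working it through.** **1. The definitions side by side**

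| Score at 3 hours | Specific aims (above 3) | Study Design (3 or more) | Success or improvement (2 or less) |
|---|---|---|---|
| 1 | not failure | not failure | yes |
| 2 | not failure | not failure | yes |
| 3 | **not failure** | **failure** | no |
| 4 | failure | failure | no |

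Under Study Design, failure and success are exact complements. Under Specific aims, a score of 3 is neither. The entry rule, the success rule and the improvement rule all fit a failure cut-off of 3 or more, so the Specific aims sentence is the outlier.

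**2. The plan's own sample size**

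Inputs from the Sample size calculation table, 50% reduction row: p1 = 0.6667 (placebo), p2 = 0.3333 (treatment), one-sided α = 0.05, power 0.80, continuity-corrected test, equal groups.

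- Uncorrected: m = [1.645·√(2·0.5·0.5) + 0.842·√(0.6667·0.3333 + 0.3333·0.6667)]² / 0.3334² = 26.7.
- Corrected: n = (m/4)·[1 + √(1 + 4/(m·0.3334))]² = 32.5, so 33 per group and 66 in total.

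This matches the plan. The figure holds only if 0.6667 and 0.3333 are rates under the cut-off actually used.

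**3. What the other cut-off could do to power (illustration)**

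Two assumptions, neither in the documents: the planning rates are rates of scoring 3 or more, and a given share of those failures score 4. The rate under the Specific aims cut-off is then the planning rate times the share. Power is by exact binomial enumeration at 33 per group. The test rejects when z = [(x1 − x2)/33 − 1/33] / √(2·p̄(1 − p̄)/33) reaches 1.645, where x1 and x2 are the placebo and cetirizine failure counts and p̄ is the pooled proportion.

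| Share scoring 4, placebo / cetirizine | Failure rates | Power |
|---|---|---|
| 100% / 100% (as planned) | 66.7% v 33.3% | 0.82 |
| 75% / 75% | 50.0% v 25.0% | 0.59 |
| 50% / 50% | 33.3% v 16.7% | 0.36 |
| 33% / 33% | 22.2% v 11.1% | 0.21 |
| 25% / 25% | 16.7% v 8.3% | 0.14 |
| 60% / 30% | 40.0% v 10.0% | 0.84 |
| 33% / 50% | 22.2% v 16.7% | 0.08 |

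**4. One dataset, two answers (hypothetical counts)**

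- 3 or more: 22/33 v 11/33. Pooled 0.5, z = (0.3333 − 0.0303)/0.1231 = 2.46, one-sided p = 0.007.
- Above 3, about half of each arm's failures scoring 4:
  - 11 v 5: z = (0.1818 − 0.0303)/0.1055 = 1.44, p = 0.08.
  - 11 v 6: z = (0.1515 − 0.0303)/0.1077 = 1.13, p = 0.13.

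The same children can fall on either side of 0.05 depending on which sentence is followed.

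**The case against.** There are three serious points on the other side.

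- **The symbol may be a reading artefact.** An underlined greater-than sign could have lost its underline when the PDF was read, and that would not be an error in the plan. This stands as a possibility, and it is why the source file comes first. It cannot be presumed, because the other greater-or-equal thresholds in the document came through intact.
- **The intended meaning can be recovered.** The success and improvement rules are complements of 3 or more. Level 3 means intervention is needed. The word persistent in Specific aims suits a child who remains in the entry state. All of this is fair, and it is why Specific aims is the sentence to correct. But that sentence is the primary objective itself, and a primary endpoint should not depend on the reader's inference.
- **The size is hypothetical.** This stands in full. If cetirizine also lessens severity among failures, power need not fall: shares of 80%/60%, 75%/50% and 70%/40% (placebo/cetirizine) give 0.83, 0.85 and 0.87 by the same calculation. The figures show that the two cut-offs can give different answers. They do not show that power is lost, and the conclusion does not rest on them.

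**Conclusion.** The concern holds. As supplied, the document gives two incompatible definitions of its sole primary endpoint, and neither is marked as governing. Every child scoring exactly 3 at 3 hours changes category between them; the documents do not give that number. Across the assumed shares tabulated in the working, power under the stricter cut-off ranges from 0.08 to 0.84, against 0.82 as planned, so the effect on power is undetermined in size and direction. The contradiction itself needs no assumption beyond the symbol being read correctly. Confidence is medium because of that one character. If the symbol stands, the point must be fixed before analysis.

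**What to change.** First check the symbol in the source file. If it is greater-or-equal there, the cut-off needs no edit. If it is greater than, amend the Specific aims sentence so that treatment failure is an itch score ≥3 at 3 hours after receiving the intervention, in line with Study Design. One cut-off then governs the primary analysis. This concerns only how the endpoint is counted; it takes no position on the discontinuation rule that Study Design attaches to failure.

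In the same edit, align the time origin. The Primary Outcome entry counts the 3 hours from randomisation, whereas the score is timed from the intervention: "Subjects will have itch scores measured at two time points from receiving the intervention, one at 3hours and other at 12 hours".

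The cost is one amendment with two small wording changes. There is no added data collection or patient burden, because the 3-hour score is already recorded on the full 1 to 4 scale. If the planning rates are rates of scoring 3 or more, the sample size stays at 33 per group; the amendment should state that reading.

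### Secondary outcome 7 compares rescue doses by arm without a counting window, although 3-hour failures leave the study just as rescue opens

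*Combined protocol and SAP*

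**What the plan says.** All of this is in the combined protocol and SAP, under Study Design and Secondary Outcomes.

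- **Rescue:** "Subjects will be allowed to receive rescue Diphenhydramine (Benadryl) 3 hours post intervention at the discretion of the treating physician".
- **Failures:** a score of 3 or more at 3 hours is a treatment failure and "will result in discontinuation from the study. Successfully treated subjects will have a second itch score measured at 12 hours post intervention".
- **Successes:** they "will continue in that arm for a maximum of 12 hours or till discharge whichever is earlier". Their 12-hour score is taken "to analyze the persistence of antipruritic effect of the intervention".
- **Recording:** a sentence beginning "The total number of rescue Benadryl doses in each group will also be" says that rescue doses are recorded. It gives no period.
- **Outcome 7:** "Number of rescue Benadryl doses between treatment and the placebo group". No start, end or population is given.
- **After the study:** "At the conclusion of the study, patients will be reassessed by the primary team for further need for any anti-pruritic medications".

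Statistical Method lists the chi-square, t and Mann-Whitney tests without assigning any of them to an outcome. It has no rule for children who have been discontinued.

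**The concern.** The children most likely to be given rescue are those still itching at 3 hours. They leave the study at the moment rescue becomes available, and the planning rates put twice as many of them in the placebo arm. Two data collectors could follow this text and return different datasets: one stopping each child's count at discontinuation, the other counting to 12 hours.

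Under the first approach, the arm with more failures is observed for less time and loses more of its rescue doses. A drug that works could then appear to need as much rescue as placebo, or more, because more of its children stay under observation.

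A related, smaller issue concerns the 12-hour score. It exists only for children selected by their 3-hour response, which is the primary outcome. A difference between arms in that subset would not be a randomised comparison.

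**Working it through.** **Inputs from the documents.** Failure rates are 0.6667 (placebo) and 0.3333 (cetirizine), with 33 per group, from the 50% reduction row of the sample size table. The test is one-sided and continuity-corrected, with α = 0.05 and power 0.80. Rescue opens at 3 hours and follow-up of successes ends at 12 hours or discharge.

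**1. The plan's own figure.** With mean rate 0.5 and difference 0.3334, the uncorrected size is n₀ = [1.645√(2 × 0.5 × 0.5) + 0.842√(2 × 0.2222)]² / 0.3334² ≈ 26.8. The continuity-corrected size is (n₀/4)[1 + √(1 + 4/(n₀ × 0.3334))]² ≈ 32.5, so 33 per group and 66 in total. The stated figure is reproduced.

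**2. Who leaves at 3 hours.** Failures are 33 × 2/3 = 22 placebo and 33 × 1/3 = 11 cetirizine. Successes are 11 and 22.

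**3. On-study time from 3 to 12 hours, with no early discharge.** Placebo has 11 × 9 = 99 child-hours and cetirizine 22 × 9 = 198. Following everyone would give 33 × 9 = 297 in each arm.

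**4. Rescue totals.** Let c be doses per failure and r doses per success, the same in both arms. These rates are assumptions; the documents give none.
- Failures' doses left out: 11r v 22r, so cetirizine is double whenever r > 0.
- All randomised: 22c + 11r v 11c + 22r. The difference is 11(c − r), so placebo is higher whenever c > r.
- Example, c = 1 and r = 0.2: 2.2 v 4.4 with failures left out, and 24.2 v 15.4 in all randomised.

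**5. Sensitivity.** Let rates differ by arm (P placebo, C cetirizine). The difference in doses per randomised child, placebo minus cetirizine, is D = (2cP + rP − cC − 2rC)/3. With rP and rC each between 0.1 and 0.5 (assumed):

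| Doses counted per failure | Range of D |
|---|---|
| 2 in both arms | 0.37 to 0.77 |
| 1 in both arms (also the result if only the first dose is caught) | 0.03 to 0.43 |
| 0 in both arms | −0.30 to +0.10 |
| cP and cC each free between 1 and 2 | (2 + 0.1 − 2 − 1)/3 = −0.30 to (4 + 0.5 − 1 − 0.2)/3 = +1.10 |

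Leaving out failures' doses removes (2cP − cC)/3 from D. That is 0.33 to 0.67 if doses per failure are equal in the two arms, and 0 to 1.0 if they differ within 1 to 2.

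**6. The 12-hour score.** It is expected in 11 placebo and 22 cetirizine children. A simulation used the planning rates at 3 hours, an equal true 12-hour failure rate of 50% in both arms, and an assumed within-child correlation. Among 3-hour successes, the 12-hour failure rates (placebo v cetirizine) were:
- 37% v 43% at correlation 0.3
- 27% v 39% at correlation 0.5
- 17% v 34% at correlation 0.7

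The apparent disadvantage of cetirizine is produced by selection alone.

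**The case against.** The strongest reply is that the full count is the more natural reading. Rescue doses are to be recorded as a group total, directly after the group total of failures, with no restriction to successes. A rescue outcome that left out failures would have little purpose. Nor does discontinuation clearly end all data capture: Study Design allows a missed baseline tryptase sample to be taken later, once the child is symptom-free, and it records opioid dosing for each subject with no cut-off at 3 hours. This stands as far as it goes. It shows that a full count is possible and perhaps intended, but neither provision concerns rescue doses.

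A second reply is that the dose rates are assumed and that a change of sign is not peculiar to a truncated count. That is right: the last row of the sensitivity table reaches −0.30 with every dose counted.

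A reader might also infer more than the text supports:
- **That the rescue comparison is biased by design.** The documents leave the window open; they do not prescribe an on-study count.
- **That a between-arm test of 12-hour scores is planned.** The 12-hour score is not a listed outcome and no such test is stated.
- **That the primary result is at risk.** The primary outcome is settled at 3 hours, before any of this applies.

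**Conclusion.** The point holds as an undefined secondary outcome that is worth amending. If on-study time limits the count, failures' doses are missed or cut short and the arms have unequal observation (22 v 11 children gone, at most 99 v 198 child-hours left). Those figures need only the planning rates and no early discharge. That such a count can shrink or reverse the rescue difference depends on assumed dose rates, so its size and direction cannot be fixed from the documents. If only failures' later doses were lost, the difference would shrink but keep its sign under the equal-rate assumptions.

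The 12-hour part is supporting. The score among 3-hour successes can describe how long relief lasts within each arm, but it cannot support a randomised comparison of persistence.

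The primary outcome and the sample size of 66 are unaffected.

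**What to change.** Leave the treatment, rescue and discontinuation rules as they are, and amend the data and analysis text.

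1. Define outcome 7 as rescue doses taken from the inpatient chart for every randomised child, from 3 to 12 hours or discharge, whatever the 3-hour status, compared by randomised arm. The Mann-Whitney test, already on the plan's general list, would serve; use a rate per hour observed if early discharge is common.
2. Label the 12-hour score among 3-hour successes as descriptive. Any between-arm statement about persistence should use all randomised children, with 3-hour failures counted as not controlled. It would add limited information: with no relapse it is simply 22/33 v 11/33, the 3-hour result again, with a 95% half-width of 1.96 × √(2 × (2/9)/33) = 0.23.
3. Minor wording: state the time point for outcome 6 (the itch score section defines improvement at 3 hours, which makes that the natural reading). Reconcile "Subjects will have itch scores measured at two time points from receiving the intervention, one at 3hours and other at 12 hours" with the later sentence that gives the 12-hour score to successes only.

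The cost is amendment wording and a short chart review for about 33 children (22 + 11 at the planning rates). The investigators should confirm that consent covers chart data after discontinuation; the consent pages are not in the public file, so this cannot be judged here. One limitation remains: after discontinuation the count partly reflects ordinary care, including other antipruritics and changes of opioid. Recording those alongside the rescue doses would help interpretation.

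### Age, race and sex effects on itch incidence (secondary outcome 4) are to be tested one factor at a time, so an apparent demographic effect may partly reflect opioid exposure

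*Combined protocol and SAP*

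**What the plan says.** Secondary Outcomes, item 4, is the "Effect of age, race, and sex on the incidence of opioid-induced pruritus". Specific aims gives the same purpose as a secondary objective: "The effect of age, race, sex on opioid induced pruritus and the influence of these parameters on antipruritic effect of the drug".

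The only analysis methods are in Statistical Method: "Data will be analyzed using Chi square, student t-tests and Mann-Whitney U test (for non-parametric data) where appropriate". No regression, stratification or covariate is named anywhere.

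Two other places concern opioid dose. Background and Significance says of itch: "The prevalence goes up with the dose of opioid being used". Study Design says: "The opioid dose, interval and total doses that each subject receives will be recorded". No listed outcome or method then uses the recorded dose.

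On who is enrolled, the inclusion criterion reads "Children age 6-18yrs on opioids who develop pruritus and are willing to participate in the study". The Subject recruitment text instead describes children "requiring treatment with oral or intravenous opioids will be recruited from the pediatric inpatient units", with no requirement that they itch.

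**The concern.** Outcome 4 is an observational comparison inside a randomised trial. Randomisation protects the comparison of cetirizine with placebo. It does nothing for a comparison of older with younger children, boys with girls, or one race with another.

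Each of the three named tests relates one factor to one outcome, and the proviso about appropriateness only chooses among them. Age, race and sex are therefore not adjusted for each other, and none is adjusted for opioid dose, which the protocol itself describes as raising the prevalence of itch.

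At stake is the reading of a stated secondary objective. If opioid exposure happens to differ between groups, a significant result could not be separated into a difference in susceptibility and a difference in exposure. A real difference in susceptibility could also be hidden. Claims about race or sex in children are easily misread, and the study intends to collect the variable that would help to interpret them.

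**Working it through.** **What the plan's own figures cover.** The documents give no sample size, effect or dose distribution for outcome 4. The stated 33 per group belongs to the primary outcome. It reproduces with failure rates 0.6667 and 0.3333, one-sided α = 0.05, 80% power and continuity correction:

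- Uncorrected n = [1.645·√(2·0.5·0.5) + 0.842·√(0.2222 + 0.2222)]² / 0.3333² ≈ 26.8, so 27 per group.
- Corrected n = (26.8/4)·[1 + √(1 + 4/(26.8·0.3333))]² ≈ 32.5, so 33 per group, 66 in total.
- 66 × 1.1 = 72.6, so 73 recruited.

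These 73 are randomised children, who by design all have an itch score of at least 3. They cannot serve as a cohort for incidence.

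**Size of a cohort that could yield incidence (assumption).** Preliminary Results reports "37% (n=6) of patients treated with opioids in the inpatient setting develop pruritus" among 16 patients: 6/16 = 0.375. Finding 73 children with itch would then take 73/0.375 = 194.7, about 195 children. This rests on 16 patients and assumes that every itching child qualifies for randomisation.

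**Illustration 1: continuous dose.** Age and dose are bivariate normal with correlation r. Age has no direct effect: logit(itch) = logit(0.37) + ln(OR) × dose, with OR 1.5 or 2 per SD. There are 195 children, and an unadjusted t-test on age at two-sided 0.05. Share of simulated studies that are significant:

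| Age-dose correlation (assumed) | Unadjusted test |
|---|---|
| 0 | about 5% |
| 0.1 | 6% to 7% |
| 0.2 | 7% to 14% |
| 0.3 to 0.5 | about 10% (r = 0.3, OR 1.5) to 58% (r = 0.5, OR 2) |

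Adjacent ranges overlap because of simulation error. For r of 0.3 to 0.5, a logistic model with age and dose gave about 4% to 5%. That model has two covariates only; the fuller model proposed below was not simulated.

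**Illustration 2: two dose levels.** The factor has no effect of its own. Itch risk is 0.25 at low dose and 0.50 at high dose (0.375 overall if half are on high dose), with 195/2 ≈ 98 children per subgroup. With share h on high dose, crude risk = 0.25(1 − h) + 0.50h.

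| High-dose share, A v B | Crude risks | Risk ratio | Chance of p < 0.05 |
|---|---|---|---|
| 50% v 50% | 0.375 v 0.375 | 1.00 | 5% |
| 60% v 40% | 0.400 v 0.350 | 1.14 | 11% |
| 70% v 30% | 0.425 v 0.325 | 1.31 | 30% |
| 80% v 20% | 0.450 v 0.300 | 1.50 | 58% |

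With a weaker dose effect (risks 0.30 and 0.45), the last three risk ratios fall to 1.08, 1.17 and 1.27, and the chances to 6%, 14% and 25%.

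Both illustrations agree: there is no distortion when dose is unrelated to the factor, and a large one when the relation is strong. The documents do not say where in that range the trial lies.

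**Is there a denominator?** Read alone, the inclusion criterion admits only children who itch, and incidence cannot then be analysed by any method. The recruitment text, the baseline tryptase draw planned before itch begins, and outcome 2 (children who itch against those who do not) all imply that children without itch are enrolled. Outcome 4 makes sense only on that second reading.

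**The case against.** The strongest reply is that a reader might infer that these results are confounded, and the documents do not show it. Confounding needs dose to differ by age, race or sex, and nothing in the protocol says that it does. A correlation of zero is not excluded, and there the unadjusted test behaves properly. This stands: the most that can be said is that the results may partly reflect dose.

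The second reply is that adjustment is not obligatory. Dose follows age, race and sex and cannot cause them. If older children itch more because they receive more opioid, dose lies on the pathway, and the unadjusted comparison is a legitimate total effect. The significant results in the first illustration are errors only if the direct effect is the target. This also stands. The plan does not say which effect it wants, and that is part of the gap.

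The third reply is that the inclusion criterion leaves no children without itch, so regression is beside the point. This stands only in part. Other parts of the protocol imply that such children are enrolled. The conflict must be settled first, but it does not remove the need for an analysis plan.

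Finally, the dose data may be less complete than they look. The recording sentence sits in the text on follow-up after the intervention, so whether it covers children without itch is unclear. Exposure up to itch onset is not listed as such.

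**Conclusion.** The gap is real and modest. Outcome 4 is a non-randomised comparison, the plan offers only one-factor tests, and a recorded variable that the protocol links to itch enters no analysis. An apparent age, race or sex effect may therefore partly reflect opioid exposure, or one of the other two factors.

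The size cannot be computed from the documents. With about 195 children and an assumed odds ratio of 1.5 to 2 per SD of dose, the chance of a significant age result without a direct age effect runs from about 5% at correlation 0 to about 58% at 0.5. Both the correlation and the odds ratio are assumptions, and the cohort size rests on a pilot of 16.

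A reader might also infer that the trial's main result is at risk. It is not: the primary comparison is randomised. Nor does the same remedy extend to outcome 5, the influence of age, race and sex on response to cetirizine. A main effect of dose in that model would not deal with confounded effect modification, so no change to outcome 5 is proposed here.

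**What to change.** 1. Reconcile the inclusion criterion with the recruitment text and with outcomes 2 and 4, so that it is clear whether children without itch are enrolled. State that opioid dose is recorded in them too.
2. For outcome 4, pre-specify as exploratory a logistic regression of itch (yes or no) on age, race and sex together, reported twice:
   - without opioid exposure, for the total effect of each factor given the other two;
   - with opioid exposure, for the effect not explained by dose.

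   State which question each version answers.
3. Define exposure as opioid received up to itch onset, or over a comparable window in children who do not itch. Do not use total doses over the whole stay: itch may itself lead to the opioid being stopped, and the total would then be partly a consequence of the outcome.
4. Keep the unadjusted tests as descriptive.

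The cost is a few lines of analysis plan, some data handling to derive exposure in a comparable window, and dose records for children without itch if these are not already planned. No further randomised patients are needed. Intervals will be wider in the fuller model because events are few: about 0.375 × 195 ≈ 73 under the assumption above, and fewer if fewer children are enrolled. That is a reason to label the analysis exploratory.
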